## Overall survival

Overall survival is defined as the time (number of days) from the start of the treatment (the date of the first dispensed package, of sunitinib or axitinib) until the date of death as documented in the Cause of Death Register. If no death is recorded, data is censored at latest available date in data.

[figure not shown]
### 8.3. Variables

Table 1 summarizes an overview of the variables needed for the outcomes and study variables of the proposed analyses.

**Table 1. Overview of study variables**

Variable	Role	Data source(s)	Operational definition
Total number of sunitinib 1L patients	Outcome	Prescription Register	Number of sunitinib users with at least one filled prescription (in total and per year over time)
Number of sunitinib 1L 4:2 schedule users	Outcome	Prescription Register	Number of sunitinib users that started on a 4:2 schedule and never had a modification in the schedule (total and per year over time)
Number of sunitinib 1L 2:1 schedule users	Outcome	Prescription Register	Number of sunitinib users that started on a 2:1 schedule and never had a modification in the schedule (total and per year over time)
Number of sunitinib 1L patients that was switched from a 4:2 schedule to a 2:1 schedule	Outcome	Prescription Register	Number of sunitinib users that started on a 4:2 schedule and later was switched to a 2:1 schedule, in total and per year over time

PFIZER CONFIDENTIAL

Total number of axitinib second line patients	Outcome	Prescription Register	Number of axitinib 2L users with at least one filled prescription (in total and per year over time)
Gender	Baseline characteristics	Prescription Register	Male/Female (binary)
Age	Baseline characteristics	Prescription Register	Age will be defined as age at the date of first filled prescription of relevant mRCC medication (continuous; years).
Year of treatment initiation	Baseline characteristics	Prescription Register	Defines the year the treatment was initiated.
Region	Baseline characteristics	Prescription Register	County council of the prescribing physician at first prescription date (categorical), see Table 6 in Annex 3
Time to treatment discontinuation	Outcome	Prescription Register	Time from date of first filled prescription to the end of the prescribed supply, or prescription of other ATC code or death if either of these happen before (details in Section 8.2).
Overall survival	Outcome	Cause of Death Register, Prescription Register	Time from date of first filled prescription of the relevant drug to date of death (number of days) where death is defined as all-cause death; If no date of death is recorded, data is censored at latest available date in data.

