## 8. RESEARCH METHODS

### 8.1. Study design

To address the research objectives, the study will be carried out as a national retrospective population-based register study based on data from the NBHW.

Based on the study objectives, the primary endpoint in this study is:

- Time to treatment discontinuation in first line sunitinib patients. Time to event measure from index date to discontinuation of treatment, from 01 July 2005 to 31 December 2019 (assessed from index date up to 180 months). This will be investigated using Kaplan-Meier analysis.

[figure not shown]

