### 8.2. Setting

The data used for the analyses includes all patients aged  $\geq 18$  years with at least one filled prescription of an oral targeted therapy relevant for treating mRCC registered in the Swedish Prescribed Drug Register between 01 July 2005 (there is no data available in the register before this date) and 31 December 2019. The Anatomical Therapeutic Chemical (ATC) codes for the oral drugs relevant for treating mRCC are the following: L01XE04 (sunitinib), L01XE05 (sorafenib), L01XE11 (pazopanib), L01XE17 (axitinib), L01XE10 (everolimus), L01XE26 (cabozantinib), L01XE34 (tivozanib), L01XE29 (lenvatinib).

Selecting patients based on dispensed prescriptions ensure that all patients that have prescriptions on the relevant drugs are included in the analyses. The first identified prescription date will correspond to the patient's index date that is relevant for capturing the age.

The PDR does not provide any information on mRCC, which is the area of interest in this study. The analysis therefore combines the PDR, the SCR and the NPR with the aim to identify the mRCC cohort. The patients identified in the PDR that also are identified in the SCR with the International Classification of Diseases and Related Health Problems

PFIZER CONFIDENTIAL

(ICD)-7 diagnosis codes I800 or I809 and ICD-10 codes C64.0 and C64.9 from 01 January 2000 until 31 December 2019; excluding ICD-7 code I801 (cancer of the renal pelvis) will be included in the analysis set.

The mRCC cohort derived above will then be further restricted into two different analysis sets that will be used to carry out the analyses.

[figure not shown]
- Analysis Set 1: patients treated with sunitinib in the first line mRCC setting
- Analysis Set 2: patients treated with axitinib in the second line mRCC setting

Analysis Set 1 will be derived in the following way, from the full mRCC cohort described above, individuals will be selected that have sunitinib as the first filled prescription (the earliest date) of the relevant drugs: (sunitinib), L01XE05 (sorafenib), L01XE11 (pazopanib), L01XE17 (axitinib), L01XE10 (everolimus), L01XE26 (cabozantinib), L01XE34 (tivozanib), L01XE29 (lenvatinib), and L03AB (cytokines medication). L03AB used to be a common treatment for this patient group in the beginning of the investigated period and is therefore needed to identify the correct treatment line.

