### Time to treatment discontinuation

Time to treatment discontinuation, or persistence, is defined as the difference between the start and end-dates for a treatment episode (accordance with the International Society for Pharmacoeconomics and Outcomes Research (ISPOR) Medication Compliance and Persistence Work Group) regardless of reason for discontinuation. The start date for a treatment episode is defined as the date of first dispensed package and the end date is defined as the date of the last dispensed package with the same ATC code, plus the number of days that package, as well as accumulated medicine (see more details below), is intended to cover. This end date is overruled if there is a new filled prescription of another relevant ATC code or death happens before this, then either of these dates represents the end date. If no end of prescribed supply is recorded, data is censored at latest available date in data.

[figure not shown]
Time to treatment discontinuation will be calculated while allowing for patient accumulation of medicine. The number of days covered by the dispensed volume will be determined based on information in the Summary of Product Characteristics (SPC), the volume of dispensed drug, and for sunitinib in first line also by using the prescriber's dosing instruction on the prescription available in the PDR.

For sunitinib, the treatment is provided in 4 + 2 (or 2 + 1) week cycles, where there is a two-week break in treatment after four weeks of continuous drug intake. Hence, the assumed number of days covered by each filled prescription will be adjusted accordingly (i.e. the 14 or 7 days corresponding to the cycle will be added).

When previously supplied dosing instructions cease to be specified, it is assumed that the daily dosage continues in accordance with the previous treatment pattern. Should there be a completeness issue with the variable containing dose information; the recommended average dose per day according to the SPC for each product will be used instead.

[figure not shown]
For axitinib, the treatment is provided in 4 week cycles, without breaks in between. The analysis relies on data on information relating to dispensed pack size and strength;

PFIZER CONFIDENTIAL

Axitinib is available in pack size of 56 tablets, and in strength 1, 3, 5 and 7 mg. Given the dosing recommendations in SPC, a dispensed pack with the strength 1 mg is assumed to last 14 days, whereas the other packs are assumed to last 28 days.

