### **8.6. Data management**

In broad terms, the data management for this study will be initiated by the creation of a broad study population including patients with at least one filled prescription of (L01XE04 (sunitinib), L01XE05 (sorafenib), L01XE11 (pazopanib), L01XE17 (axitinib), L01XE10 (everolimus), L01XE26 (cabozantinib), L01XE34 (tivozanib), L01XE29 (lenvatinib)) identified in the PDR. A study key including the selected cases personal identifiable number (PIN) and a randomly created study identification number will be created by the NBHW. The data that is being extracted from the NBHW is described in Table 3 below.

PFIZER CONFIDENTIAL

Based on the data extracted from the NBHW two completely pseudonymized analytical dataset comprising all observations and variables required for the planned analyses will be compiled, see details in Section 8.2. The analytic datasets will be person-level.

[figure not shown]
All data management will be performed by ICON. A data validity quality check is always undertaken before data management is started to verify that all variables are complete and to create logs for corrupt or ambiguous data entries. Data will be analyzed using SAS version 9.2 or later.

One of the variables included in the material (DOSER) is in text format, requiring human review. The information in DOSER will be reviewed for Analysis Set 1 (patients identified with sunitinib treatment in first line) and used to identify the initial dosing schedule and changes in the dosing schedule. The information in DOSER will be quantified in the following way. DOSER will be lifted out to an excel sheet together with study IDs and drug dispense dates. DOSER will be manually reviewed and dummy variables indicating the dosing schedule and dates for changes in the dosing schedule will be created. When the manual coding is done, the data will be merged with the original dataset based on the study IDs.

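### Yearly counts of switched and never-modified sunitinib patients have no follow-up window, so the last start years (mainly 2019, partly 2018) would show too few switchers and too many never-modified patients

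*Combined protocol and SAP*

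**What the plan says.** Section 8.3, Table 1, gives the role of outcome to three schedule counts in first-line sunitinib: patients who started on 4:2 and were never modified, patients who started on 2:1 and were never modified, and patients who moved from 4:2 to 2:1. The never-modified rows count patients who "never had a modification in the schedule (total and per year over time"). The switcher row counts those who "later was switched to a 2:1 schedule, in total and per year over time". The table does not say which year is meant. The only year variable it defines is the year of treatment initiation.

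Section 8.2 admits patients with a first filled prescription "between 01 July 2005 (there is no data available in the register before this date) and 31 December 2019". Entry and data therefore close on the same day. The Dosing Schedule definition in section 8.2.1 bases a switch on the prescriber's instruction and sets no time limit.

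For treatment duration, section 8.2.1 states: "If no end of prescribed supply is recorded, data is censored at latest available date in data". Overall survival has a matching rule. The counts have none. Section 8.6 says that "dummy variables indicating the dosing schedule and dates for changes in the dosing schedule will be created", so the timing of each change will be known. Section 8.9 does not mention unequal follow-up by start year.

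**The concern.** Whether a patient was ever switched is known only once treatment has ended or the switch has happened. A patient who started on 4:2 in autumn 2019 and was still on it at the data end would be counted as never modified, although the final status is unknown. A patient who started in 2012 has usually had time to show it. Tabulated by start year, the two labels therefore mean different things in early and late years: patients who will switch later sit among the never-modified in the most recent rows.

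Those rows are the ones a reader would use to judge current practice. A drop in switchers there could come from the data cut alone. Nothing planned corrects it: year of initiation as a Cox covariate (section 8.7) does not change a table of counts.

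**Working it through.** **The plan's own follow-up figure.** Section 8.1 gives the window "from 01 July 2005 to 31 December 2019 (assessed from index date up to 180 months"). From 1 July 2005 to 31 December 2019 is 14.5 × 12 = 174 months. The stated 180 is worded as an upper limit and does not affect this point. The plan states no switching rate, time to switch or median treatment duration, so there is no planned figure to reproduce.

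**Follow-up available by start year.** From the dates in section 8.2: 2019 starters 0–12 months (mean 6), 2018 starters 12–24 (mean 18), 2017 starters 24–36, and 2005 starters up to 174.

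**Share of eventual switches visible at the cut.** Assumptions (none from the documents): starts spread evenly within each year; a constant hazard λ for the first of switch or end of treatment (stopping or death); the same eventual switch share in every start year, so no true trend. With m the median in months, λ = ln 2 / m. For follow-up evenly spread from a to a + 12 months,

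visible share = 1 − [exp(−λa) − exp(−λ(a + 12))] / (12λ).

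For m = 6, 12λ = 1.386. For 2019, 1 − (1 − 0.25)/1.386 = 0.459. For 2018, 1 − (0.25 − 0.0625)/1.386 = 0.865. The eventual switch share cancels out.

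| Start year | m = 3 | m = 6 | m = 12 | m = 18 |
|---|---|---|---|---|
| 2019 | 66% | 46% | 28% | 20% |
| 2018 | 98% | 86% | 64% | 50% |
| 2017 | 100% | 97% | 82% | 68% |
| 2016 | 100% | 99% | 91% | 80% |

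**Separate hazards as a check.** Assume monthly hazards of 0.05 for a switch and 0.08 for stopping or death first. The eventual switch share is 0.05/0.13 = 38.5%. The share seen by the cut is 19.0% for 2019 starters, 34.4% for 2018 and 37.6% for 2017. Over switch hazards of 0.02–0.10 and stop hazards of 0.06–0.12, the visible fraction is 36–65% for 2019 and 75–97% for 2018, inside the range of the table.

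**In patients.** Section 8.5 expects about 1,000 first-line sunitinib patients; 1,000/14.5 ≈ 69 starters a year if evenly spread. If all began on 4:2 and 30% eventually switched (both assumed), that is 20.7 switchers a year. The 2019 count would be 13.7, 9.5, 5.8 or 4.1 for m = 3, 6, 12 or 18, a shortfall of 7 to 17. The 2018 count would be 20.3, 17.9, 13.2 or 10.3, a shortfall of 0.4 to 10.4. Patients missing from the switcher row would mostly appear as never modified.

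**Does a fixed time point remove it?** A simulation used 200,000 patients per start year, a 30% eventual switch share and m = 6. The 6-month figure is the Aalen-Johansen cumulative incidence, with end of treatment as competing event; its true value is 0.30 × (1 − 0.5) = 15.0%.

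| Start year | Ever switched by the cut | Switched by 6 months |
|---|---|---|
| 2015 | 30.1% | 15.1% |
| 2016 | 29.7% | 15.0% |
| 2017 | 29.1% | 15.1% |
| 2018 | 25.8% | 14.9% |
| 2019 | 13.9% | 15.0% |

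The artificial fall disappears.

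**Which year is meant?** By year of initiation, the switcher and never-modified counts are both affected. By year of switch, every switch up to the cut is counted in its year, so the switcher row is complete. The never-modified rows are still affected, because that label always depends on follow-up to the end of treatment.

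**The case against.** The best defence is that the table is descriptive and the effect is confined. Table 1 lists counts; section 8.7 plans no switching share, trend estimate or test by year; Tables 4 and 5 contain no yearly output; and section 7 does not list schedule uptake as an objective. The switcher row can be read as switches occurring in each year, which needs no correction. Every size above rests on assumed hazards. If patients switch or stop quickly, long administrative follow-up adds little and only 2019 is materially affected. A defined year and a footnote might be enough.

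Most of this stands as a limit on reach. It does not remove the problem: year of initiation is the only year the plan defines, the never-modified rows are affected even under the year-of-switch reading, and the direction requires only that some switches fall after the cut.

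Some stronger readings are tempting but not supported:

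- *The whole trend in schedule use is distorted.* Years before 2018 are little affected unless switching is late. Yearly counts also depend on how many patients start each year, which the documents do not give, so a reported fall in switchers cannot be predicted with certainty.
- *Every reading of the yearly count is wrong.* The year-of-switch reading gives a complete switcher count. Nothing says that patients would be counted as switchers in years before they switched.
- *The coded change dates serve no output.* Section 8.2.1 sets the days covered for sunitinib from the dosing instruction and the cycle, so the schedule history appears to feed treatment duration. What is missing is an output on the timing of switching.

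**Conclusion.** The point holds for the last start years. As written, Table 1 applies whole-course labels to patients with as little as no follow-up, and by year of initiation it under-counts switchers and over-counts never-modified patients, mainly for 2019 and to a lesser extent for 2018. The visible share of eventual switches is about 20–66% for 2019 and 50–98% for 2018, assuming constant hazards, even entry within the year and a median of 3 to 18 months to switch or end of treatment. The documents cannot narrow that range. The counts are descriptive and the primary endpoint is not touched, so this should be corrected but does not threaten the main analysis.

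**What to change.** In Table 1:

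1. Define the yearly breakdown as year of treatment initiation.
2. Report the number of starters per year by initial schedule. This is known at the start and needs no follow-up.
3. Keep the three whole-course groups as totals only, labelled as status at 31 December 2019.
4. Report switching by start-year band as the cumulative incidence of a 4:2-to-2:1 change at 6 and 12 months from first dispensing. Use the Aalen-Johansen estimator, with discontinuation or death before the change as competing event and censoring at 31 December 2019. The change dates come from the coding in section 8.6.
5. If yearly whole-course counts are kept, flag 2018 and 2019 as incomplete and say why.

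The cost is one changed table, one short programme and no new data. The price is coarser calendar detail: with roughly 69 starters a year, bands of more than one year are needed, and since 2019 starters have at most 12 months of follow-up, the 12-month figure for the latest band will rest largely on earlier starters within it. Incidence by 6 or 12 months is also lower than the eventual switch share, so it should be labelled as what it is.

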**Table 3. Variables extracted from the NBHW**

Variable	Explanation	Data source(s)
ICD7	ICD-7 code	Swedish Cancer Register
ICD9	ICD-9 code	Swedish Cancer Register
ICDO10	ICD-O/2-10	Swedish Cancer Register
ICDO3	ICD-O/3	Swedish Cancer Register
ALDER	Age at diagnosis	Swedish Cancer Register
M	Spread of tumor at diagnosis, distant metastases	Swedish Cancer Register
N	Spread of tumor at diagnosis, Lymph nodes	Swedish Cancer Register
DIADAT	Date of RCC diagnosis	Swedish Cancer Register
DODSDAT	Date of death	Swedish Cancer Register
DODSDATN	Date of death numeric	Swedish Cancer Register
KON	Gender	Swedish Cancer Register
SJUKHUS	Hospital where diagnosis was set	Swedish Cancer Register
DODSDAT	Date of death	Swedish Cause of Death Register
ALDER	Age at visit	National Patient Register
AR	Year of visit	National Patient Register
MVO	Medical focus area	National Patient Register
SJUKHUS	Hospital	National Patient Register
DIAGNOS	Diagnosis	National Patient Register
HDIA	Main diagnosis	National Patient Register
KON	Sex	National Patient Register

PFIZER CONFIDENTIAL

INDATUMA	Date for start of visit	National Patient Register
OP	Surgery	National Patient Register
UTDATUMA	Date for end of visit	National Patient Register
VTID	Duration of care	National Patient Register
ALDER	Age at the end of the year	Swedish Prescribed Drug Register
ARBLAN	The region of the prescribing clinic	Swedish Prescribed Drug Register
FDATE	Prescription date	Swedish Prescribed Drug Register
EDATE	Dispense date	Swedish Prescribed Drug Register
ANTAL	Number of packages	Swedish Prescribed Drug Register
DOSER	Dosing instructions	Swedish Prescribed Drug Register
EXPLAN	Region/County of dispensing pharmacy	Swedish Prescribed Drug Register
FVARUNR	Dispensed drug goods number	Swedish Prescribed Drug Register
ATC	ATC code	Swedish Prescribed Drug Register
PRODUKT	Name of product	Swedish Prescribed Drug Register
FORPS	Package size	Swedish Prescribed Drug Register
STYRKALF	Strength of the product	Swedish Prescribed Drug Register
STYRKAENHET	Unit of the strength	Swedish Prescribed Drug Register
KON	Gender	Swedish Prescribed Drug Register

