**Table 4. Time to treatment discontinuation and OS, first line treatment with sunitinib**

	L01XE04 Started on 4:2 schedule, no switch N=xxx	L01XE04 Started on 4:2 schedule, switch to 2:1 schedule N=xxx	L01XE04 Started on 2:1 schedule N=xxx
Censored n (%)	xx (xx.x)	xx (xx.x)	xx (xx.x)
Failed n (%)	xx (xx.x)	xx (xx.x)	xx (xx.x)
Survival time (Unit)			
Median (KM)	xx.x	xx.x	xx.x
95% CI of median (KM)	xxx.x ,xxx.x	xxx.x ,xxx.x	xxx.x ,xxx.x
Q1, Q3 (KM)	xxx.x ,xxx.x.	xxx.x ,xxx.x.	xxx.x ,xxx.x
Min , Max	xx.x ,xx.x	xx.x ,xx.x	xx.x ,xx.x
Kaplan-Meier survival point estimates – n at risk, % (95% CI)			
1 unit	x, x.xx (x.xx,x.xx)	x, x.xx (x.xx,x.xx)	x, x.xx (x.xx,x.xx)
2 unit	x, x.xx (x.xx,x.xx)	x, x.xx (x.xx,x.xx)	x, x.xx (x.xx,x.xx)
.	.	.	.
.	.	.	.
.	.	.	.
n units	x, x.xx (x.xx,x.xx)	x, x.xx (x.xx,x.xx)	x, x.xx (x.xx,x.xx)

PFIZER CONFIDENTIAL

[figure not shown]
The Table 5 below displays the output from the time to treatment discontinuation and overall survival analyses that will be carried out based on Analysis Set 2. Output will also be presented as KM curves.

To explore potential determinants drug survival and to adjust for differences across cohorts, semi-parametric cox-proportional hazard models will be deployed based on the following covariates: age, gender, year of treatment initiation, region.

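### For second-line axitinib, age is fixed at first-line start rather than axitinib start, region and year are not tied to a drug, and the Cox model leaves out the first dispensed drug and the first-line interval

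*Combined protocol and SAP*

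**What the plan says.** **Index date and age.** Section 8.2 gives each patient a single index date, based on the listed oral drugs taken together: "The first identified prescription date will correspond to the patient's index date that is relevant for capturing the age". Table 1 repeats the rule for age: "Age will be defined as age at the date of first filled prescription of relevant mRCC medication". In the drug register, the age variable to be extracted (Table 3) is "Age at the end of the year".

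**Region and year.** Table 1 takes region as "County council of the prescribing physician at first prescription date" and describes year of treatment initiation as "Defines the year the treatment was initiated". Neither entry says which drug is meant.

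**Time origin.** Section 8.2.1 starts a treatment episode at the first dispensed package of the drug concerned. It starts overall survival at the first package of sunitinib or axitinib.

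**Set 2 and its model.** Section 8.2 requires axitinib to be the second of the listed drugs and excludes patients with cytokines dispensed before it. For this set, section 8.7 (between Tables 4 and 5) says that "semi-parametric cox-proportional hazard models will be deployed based on the following covariates: age, gender, year of treatment initiation, region", with the aim of exploring determinants of drug survival. Section 8.5 expects about 300 such patients.

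**The concern.** In Analysis Set 1 the index date and the sunitinib start are the same day, so the age rule does no harm. In Analysis Set 2 they cannot be the same day: the index date belongs to the earlier drug and the survival clock starts with axitinib. Baseline age then describes the patient at a different moment from the one at which follow-up begins. The discrepancy is the time from first-line start to axitinib start, so it is larger for patients who went longer before axitinib and is not random noise.

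The model for this set contains no term for what preceded axitinib or for how long the patient went before needing it. Recorded age is age at axitinib start minus that interval, so an omitted interval with prognostic value can enter through the age coefficient. At stake are the description of the axitinib cohort at baseline and the interpretation of the exploratory Cox model. Separately, two programmers could date region and year differently and both comply with Table 1.

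**Working it through.** The plan gives no power or event calculation for Set 2. The figure of about 300 is a bare estimate, so there is nothing to reproduce.

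**1. Dates side by side**

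| Item | Date for Set 2 | Where |
|---|---|---|
| Age | First filled prescription of any relevant mRCC drug, i.e. first-line start | 8.2, Table 1 |
| Region | First prescription date, drug not named | Table 1 |
| Year | Start of the treatment, drug not named | Table 1 |
| Gender | Does not depend on the date | Table 1 |
| Start of both outcomes | First axitinib package | 8.2.1 |

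Only age is clearly misdated. Region and year are ambiguous.

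**2. Size of the age offset.** Let d be the time from first-line start to axitinib start. The documents give no distribution for d. Assume 3 to 36 months: 3/12 = 0.25 year to 36/12 = 3 years. Year-end age adds 0 to 1 year. Recorded age minus age at axitinib start then lies between 0 − 3 = −3 years and 1 − 0.25 = +0.75 year.

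**3. Effect on the age coefficient.** Let the log hazard be βA + γd, where A is age at axitinib start. Recorded age is R = A − d (ignoring the year-end error), so the log hazard equals βR + (β + γ)d. With d in the model, the coefficient of R is still β. With d left out, and A and d independent, a linear approximation gives for R:

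β − (β + γ)w, where w = Var(d) / (Var(A) + Var(d)).

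Inputs, all assumed: SD of age 9 years (variance 81); β = ln 1.02 = 0.0198, so the true hazard ratio per 10 years is 1.02^10 = 1.219; d exponential with median 0.5, 1 or 2 years (mean = median/ln 2, variance = mean squared); γ = 0 or −0.15 per year.

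Example, median 2 years and γ = −0.15: the variance is (2/0.693)² = 8.325 and w = 8.325/89.325 = 0.0932. The coefficient is 0.0198 + 0.1302 × 0.0932 = 0.0319, and exp(0.319) = 1.376.

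A simulation on the same inputs (300 patients, 150 runs per scenario, Cox models with age alone or age plus d) gave these hazard ratios per 10 years of age:

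| Median d (y) | γ | w | Approximation, first-line age | Simulated, axitinib age | Simulated, first-line age | Simulated, first-line age + d |
|---|---|---|---|---|---|---|
| 0.5 | 0 | 0.006 | 1.217 | 1.217 | 1.215 | 1.217 |
| 1 | 0 | 0.025 | 1.213 | 1.205 | 1.200 | 1.206 |
| 2 | 0 | 0.093 | 1.197 | 1.221 | 1.199 | 1.222 |
| 0.5 | −0.15 | 0.006 | 1.229 | 1.218 | 1.228 | 1.222 |
| 1 | −0.15 | 0.025 | 1.259 | 1.218 | 1.261 | 1.228 |
| 2 | −0.15 | 0.093 | 1.376 | 1.208 | 1.354 | 1.233 |

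The two ages correlate at 0.95 to 0.997. With γ = 0, misdating shifts the hazard ratio by at most 1.221 − 1.199 = 0.022. With γ = −0.15 and d omitted, the shift is 0.010, 0.043 and 0.146. Including d brings the estimate back near 1.219.

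**4. Room in the model.** Table 6 lists 21 regions, i.e. 20 degrees of freedom. With age, gender and linear year this makes 20 + 3 = 23. A binary first drug plus d makes 25. At an assumed 200 to 300 events, events per parameter go from 200/23 = 8.7 and 300/23 = 13.0 to 200/25 = 8.0 and 300/25 = 12.0.

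**5. Availability.** Table 3 already lists the ATC code and dispense date. The first dispensed drug and d need nothing more. In particular, d needs no assumption about how many days a pack covers.

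**The case against.** The strongest reply is that this is an explorative, descriptive study in which axitinib is a secondary objective. Kaplan-Meier output in Table 5 meets that objective and uses none of these covariates. The choice of exploratory covariates is then a matter of judgement, and a small error in age hardly matters. Most of this stands. It limits the weight of the point, but it does not make the stated age rule right for Set 2.

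One could also read the relevant medication in Table 1 as the drug of the analysis set, i.e. axitinib. Section 8.2 speaks against this, because its index date for age is the first prescription among all the listed drugs.

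Four stronger readings are tempting, and the documents do not support them:
- A reader might infer that the determinants in general are measured at the wrong time. Only age is; region and year are unspecified and gender is fixed.
- A reader might infer that treatment history is ignored. It defines Set 2 (second in sequence, no earlier cytokines) and is missing only from the model and tables. Section 8.9 discloses that line of treatment rests on chronological order.
- A reader might infer that age is always too low. Year-end age can outweigh a short interval, as step 2 shows.
- A reader might infer that first-line drug and duration are known for everyone. Section 8.9 says that medication given in hospital is not captured, so the first dispensed drug need not be the true first-line drug. Section 8.2.1 sets out specific days-covered rules only for sunitinib and axitinib, so the interval between starts is safer than a derived duration.

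The planned model is also already large because of region. Two further terms add little to that, but they do not relieve it.

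**Conclusion.** The point holds in a limited form. As written, the plan records Set 2 age at first-line start while both axitinib outcomes start at the first axitinib package. It leaves the date of region and year open, and it omits two derivable covariates from a model intended to explore determinants.

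The consequence is modest. Unadjusted Kaplan-Meier results are unaffected, so a claim that the axitinib survival curves are biased would go too far. Misdating age alone moves its hazard ratio per 10 years by about 0.02 at most. The larger distortion, up to 1.354 against 1.208, needs an omitted prognostic interval and the longest assumed first-line period. These figures rest on assumed values for the spread of age, its effect, the interval distribution and the prognostic slope, on independence of age and interval, and on models without gender, year or region. None of these inputs comes from the documents. The change is worth making because it corrects a stated rule at almost no cost.

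**What to change.** In Table 1 and section 8.7, define the Set 2 index date, age, region and year of initiation at the first dispensed axitinib package. Leave Set 1 as it is.

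Add two variables to the Set 2 baseline table and exploratory Cox models: first dispensed mRCC drug (sunitinib versus other) and time from first-line start to axitinib start (continuous). With age dated at axitinib start, the coefficient of the interval is γ itself and not β + γ.

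Cost: protocol wording and two variables derived from data already extracted, with about 2 degrees of freedom on top of about 23 in roughly 300 patients. Two limits remain and should be stated: earlier hospital-administered therapy stays invisible, and age stays approximate because the drug register holds it at year end.

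Optional: split Table 5 by first dispensed drug, and drop the wording about adjusting across cohorts for Set 2, where Table 5 has a single cohort.
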